Accordingly, this objective encompasses the implementation of a clinical trial **with two intervention groups (experimental and control)** designed to evaluate the effect

of a personalized intervention combining the benefits of 4D body modeling and virtual reality techniques with a dietary-nutritional treatment based on the Mediterranean Diet. The intervention aims to enhance motivation for change, treatment adherence, and health parameters in overweight and obese patients.

Furthermore, this study will allow systematic collection of clinical, anthropometric, nutritional, and psychological data, which will be integrated into the multidimensional predictive model to improve its precision and personalization capabilities.

Specifically, the clinical trial includes the following specific aims:

- To study how a 4D computer vision model combined with virtual reality technology can improve clinical assessment, the analysis of temporal morphological changes of the human body, and adherence to dietary-nutritional treatment.
- To evaluate whether adherence to an intensive multifactorial dietary-nutritional treatment based on the Mediterranean Diet, supported by immersive 4D virtual reality technology, leads to improvements in cognitive functioning.
- To analyze the impact of a nutritional intervention program based on the Mediterranean Diet and the use of virtual reality on body image perception.
- To determine whether a combined intensive intervention—based on the Mediterranean Diet and 4D virtual reality technology—can improve patients' overall health.

6. Methodology

The intervention follows a multidisciplinary approach that combines clinical, psychological, and technological assessment of overweight or obese patients, using innovative tools based on 3D body reconstruction and predictive modeling.

Challenges to Address and Technical Phases

1. 3D Model Acquisition

3D images of the body are captured from multiple viewpoints using RGB-D sensors, due to their precision, low cost, and portability. The images are aligned using articulated rigid registration techniques, enabling the construction of a complete body model. The research team has developed advanced RGB-D camera alignment methods, optimizing accuracy under real-world capture conditions [22–24].

2. 4D and Predictive Model Generation

Starting from 3D models obtained at different stages of the treatment, deformable

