The project is multidisciplinary, with multiple disciplines collaborating to achieve the common goal of improving motivation and long-term adherence to dietary-nutritional treatments. The research team has a strong track record in 3D image capture and processing, RGB-D sensor calibration and registration [22–27], as well as realistic modeling and visualization. The team also includes professionals in nutrition, psychology, and clinical assessment with experience in national and European projects focused on obesity, treatment adherence, and mental health.

Ethical Considerations

The study was approved by the Research Ethics Committee of the University of Alicante (code UA-2021-11-18, dated 18/11/2021). Prior to study participation and data collection, all participants provided written informed consent. Data will be handled in accordance with the GDPR and LOPDGDD regulations, with anonymization implemented through unique participant codes.

The following sections describe the study design, selected population, eligibility criteria, sampling strategy, sample size calculation, definition of included variables, measurement instruments, monitoring plan, and analysis strategies, along with potential limitations.

Study Design

A prospective longitudinal design with two assessment points was implemented: baseline (pretest) and post-intervention (posttest) after six months of treatment. The study comprised two groups: control and experimental. The control group received nutritional and physical activity education based on recommendations from a nutritionist. The experimental group received a specific, individualized dietary-nutritional intervention program combined with 4D virtual reality. Both groups were assessed for cognitive, clinical, and nutritional outcomes at baseline (pretest) and after six months of intervention (posttest).

To ensure sample representativeness and the generalizability of results, the sample size was calculated using the G*Power 3.1 statistical software. A statistical power of 80%, a medium effect size (0.5), and a significance level (α) of 0.05 were established. Under these parameters, at least 35 participants per group were required to carry out the intervention.

Selected Population

The sample consisted of a total of 133 Spanish volunteers, both men and women, aged between 22 and 67 years ($M = 47.11$ years; $SD = 9.38$). Participants were randomly assigned to one of the two groups (experimental or control).

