intervention. Anthropometric data and 4D images were also collected at both time points, as well as during individual follow-up sessions conducted to monitor progress and prevent relapses.

Monitoring Plan:

Potential adverse effects arising from the use of Virtual Reality (e.g., dizziness, discomfort, anxiety) and the dietary program (e.g., malnutrition, minor side effects) will be monitored. Adverse events will be recorded in a dedicated database and reported to the Ethics Committee if they are serious or unexpected. Participants will also have the right to withdraw from the study at any time without any consequences.

Data Analysis:

Data analysis is structured in two main phases, encompassing both the development of the predictive model and its clinical and psychological validation. A mixed strategy of advanced quantitative and computational analysis will be applied.

Data Preparation and Preprocessing

- Cleaning of clinical, anthropometric, psychological, and neuropsychological data.
- Standardization and normalization of variables (e.g., assessment scales, physical measurements).
- Coding of categorical variables (e.g., sex, experimental/control group).
- Outlier control and analysis of missing data (intent-to-treat analysis will be applied if missing data exceed 30%).

Classical Statistical Analysis

- **Between-group comparisons (control vs. experimental):**
 - t-tests or ANOVA for continuous measures.
 - Chi-square tests for categorical variables.
 - ANCOVA to adjust for covariates (age, sex, baseline BMI).
- **Longitudinal analysis:**
 - Repeated measures models (repeated measures ANOVA or mixed models).

- Study of changes between assessment points (0 and 6 months).

Multidimensional Predictive Modeling

- Use of multivariate regression models and machine learning to predict:
 - Body evolution (based on SMPL/STAR models).
 - Clinical parameters and psychological well-being.
 - Levels of adherence and motivation.
- Model training using data from the first period (M9) and validation in the second period.

Analysis of Predictive Psychological Variables

- Correlations between cognitive functions and adherence levels.
- Logistic/multiple regression analyses to identify significant predictors of therapeutic success.
- Evaluation of the mediating effect of psychological variables on physical and clinical changes.

Tools and Software

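### No primary outcome is designated, no multiplicity control or exploratory label is stated, and motivation, an evaluated target, has no named instrument

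*Combined protocol and SAP*

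**What the plan says.** **Outcomes.** Section 5 introduces the trial's aims with "Specifically, the clinical trial includes the following specific aims" and lists four, unranked. Section 6, Intervention Effect Analysis, gives four effects to be assessed, also unranked: motivation, treatment adherence, cognitive function and psychological well-being. Study Design adds: "Both groups were assessed for cognitive, clinical, and nutritional outcomes at baseline (pretest) and after six months of intervention (posttest". The words main, general and primary are attached only to objectives or aims, never to an outcome.

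**Power.** Study Design gives the single statement "A statistical power of 80%, a medium effect size (0.5), and a significance level (α) of 0.05 were established". It names no outcome, test or sidedness.

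**Analysis.** Data Analysis offers "t-tests or ANOVA for continuous measures", then "ANCOVA to adjust for covariates (age, sex, baseline BMI"), then "Repeated measures models (repeated measures ANOVA or mixed models"). It does not say which measure goes with which method. The ANCOVA covariates do not include the outcome's own baseline value. A further item is "Logistic/multiple regression analyses to identify significant predictors of therapeutic success", and therapeutic success is defined nowhere. No hierarchy, adjustment or exploratory label is given.

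**Motivation.** It is a target in Specific Objective 3, in Intervention Effect Analysis (which also promises questionnaires on motivational status) and in Multidimensional Predictive Modeling. The instruments named under Description of Variables are PREDIMED, IPAQ, 24-hour recalls, a food frequency questionnaire, CogniFit, TAP, CCE, ISP-20, BIS, SF-12, BDI-II, SWLS and MBSRQ. None is described as measuring motivation.

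**The concern.** A randomised comparison with a stated 5% error rate and 80% power should say which hypothesis those figures belong to. Here they belong to none. An analyst who follows Data Analysis as written, at the only stated significance level, can run many unranked comparisons by more than one method. Any one that falls below 0.05 could then be read as evidence that the visualisation helps. Nothing in the plan would distinguish such a result from a planned one.

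Motivation is a separate gap. It is central to the rationale, but a reader of the results could not check a motivation finding against a measure fixed beforehand.

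**Working it through.** **1. The plan's own figure.** The power inputs are given with at least 35 participants per group. Read as a two-group, two-sided t-test with a standardised effect of 0.5, they need 64 per group, so 35 is not reproduced. That is a separate matter and nothing below uses it.

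**2. How many outcomes might be tested.** The plan does not say, so four counts from its own lists are used.
- 4: the four effects in Intervention Effect Analysis, one score each. Motivation is counted although it has no instrument.
- 9: the cognitive, clinical and nutritional outcomes in Study Design. 1 CogniFit + 5 clinical + 3 nutritional (PREDIMED, recalls, food frequency), one score each assumed.
- 32: 15 anthropometric (height excluded) + 5 clinical + 4 nutritional and lifestyle + 1 CogniFit + 6 psychological (premorbid IQ excluded) + 1 body image.
- 56: 15 + 5 + 4 + 22 CogniFit domains + 8 psychological (the three impulsivity subscales counted separately) + 2 body-image parts.

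**3. One test per variable, no true effect, two-sided 0.05.** The expected number of false positives is 0.05m. Under independence the chance of at least one is 1 − 0.95^m. With a common correlation ρ between jointly normal statistics it is

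1 − ∫ [Φ((1.96 − √ρ·u)/√(1−ρ)) − Φ((−1.96 − √ρ·u)/√(1−ρ))]^m φ(u) du.

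The documents give no correlations; the values of ρ are assumed.

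| m | Expected | ρ = 0.7 | ρ = 0.5 | Independent |
|---|---|---|---|---|
| 4 | 0.2 | 13.0% | 15.6% | 18.5% |
| 9 | 0.45 | 20.2% | 26.9% | 37.0% |
| 32 | 1.6 | 34.7% | 52.1% | 80.6% |
| 56 | 2.8 | 41.9% | 64.8% | 94.3% |

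**4. More than one analysis per variable.** Data Analysis allows this. Suppose each variable gets a post-only t-test and a baseline-adjusted ANCOVA, with an assumed baseline correlation r = 0.5. With no true effect the two statistics correlate at √(1 − r²) = √0.75 = 0.866, and the chance that at least one is below 0.05 is 0.0734 per variable. With independent variables, 1 − (1 − 0.0734)^m gives about 50%, 91% and 99% for m = 9, 32 and 56. The independence column in step 3 is therefore not an upper limit for this plan.

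**5. Price of an optional Holm step after the primary.** Assumed: 133 split 67 and 66, no losses, 0.5 SD on both outcomes, three secondary outcomes. The noncentrality is 0.5 × √(67 × 66/133) = 2.883 on 131 degrees of freedom.
- Unadjusted power is 0.816 at 0.05 and 0.676 at 0.05/3 = 0.0167. With independent outcomes, 0.816 × 0.676 = 0.552.
- With outcomes correlated at 0.5 to 0.7, the joint chance is about 61–63%.
- Baseline adjustment raises it. At r = 0.5 with independent outcomes, 0.911 × 0.815 = 0.743.

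**The case against.** The best defence is that this is largely a technology project. Its stated main objective is to build a 4D body model, with effects on motivation and adherence studied in addition, so exploratory testing would be natural. That is fair context and limits how serious the point is. It does not remove it: section 5 calls this a clinical trial designed to evaluate the effect of an intervention, and section 6 randomises participants and claims power. If the comparisons are exploratory, the document should say so.

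A second defence is that the plan never says every listed variable will be tested. This stands. The Summary and Intervention Effect Analysis give a scope at domain level, so the illustration has to start at four outcomes and not only at the long lists.

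A reader might infer more than the documents support:
- That the trial's error rate is 81% or 94%. Those figures assume independence and one test on every listed variable. Related measures will be correlated (BMI is calculated from weight), which lowers them; repeated analyses of a variable raise them. They are neither estimates nor ceilings.
- That results have been picked selectively. Design and variables are described largely in the past tense and the analysis in the future; neither shows that outcomes have been compared.
- That adherence also lacks a measure. PREDIMED is named for Mediterranean-diet adherence.
- That success for an individual patient is left undecided. A primary outcome decides a question about groups, so its absence has no bearing on that.

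**Conclusion.** The point holds in three parts: no primary outcome, no multiplicity control or exploratory label, and no named motivation instrument. All three rest on reading the document and not on the arithmetic. The size is conditional. With one test per variable, the chance of a false positive somewhere runs from 13% (four outcomes, correlation 0.7) to 94% (56 independent outcomes), and it can be higher if several analyses are run on each. Even the smallest figure is more than twice the nominal 5%. The number of tests and all correlations are assumptions.

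This should be corrected. It does not show that the sample is too small or that any effect is spurious.

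**What to change.** **If between-group outcome data have not been examined:** the investigators designate one primary outcome before analysis. Test it once at two-sided 0.05 by ANCOVA, adjusting for that outcome's own baseline value as well as age, sex and baseline BMI. Label all other comparisons exploratory, psychological well-being included. If more than one confirmatory claim is wanted, name a short secondary list beforehand with a stated procedure, for example Holm after a significant primary. That is an option; a single primary is enough to cure the defect.

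**If the data have been examined:** label all outcome comparisons exploratory and any choice of primary post hoc.

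**Motivation:** name the instrument if one was used. Otherwise state that motivation was not measured and make no claim on it.

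**Cost:** no new participants or visits, because the baseline values are already part of the design. Confirmatory claims shrink to the primary, and to none in the post hoc case. Dropping motivation narrows Specific Objective 3, which should be acknowledged. With the optional Holm step, the chance of passing both the primary and the strictest step is the 55–63% of working step 5 without baseline adjustment, and higher with it; losses to follow-up would lower it.

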- **Statistics:** IBM SPSS Statistics for Windows v.21.0 (IBM Corp, Armonk, NY; 2012), R (latest stable version), and Python 3.11.9 with SciPy and Statsmodels libraries.
- **Machine Learning and Predictive Modeling:** Scikit-learn for classical models and preprocessing. TensorFlow and PyTorch for developing deep learning models and neural networks, including generative networks (GANs) for 3D modeling and multidimensional analysis.
- **Visualization and Clinical Analysis:** Unity 3D for integration and immersive virtual reality visualization, Blender for 3D model manipulation and creation, and internally developed modules for project-specific VR systems.

Potential Limitations

- Possible selection bias (motivated volunteers).
- Loss to follow-up in a 6-month intervention.

- Limited generalizability to the Spanish population with specific sociodemographic characteristics.
- Risk of novelty effect with VR (results may reflect the appeal of the technology rather than the actual intervention effect).

7. Expected impact

In the ICT field, the project will provide methods and algorithms to advance the analysis and prediction of morphological evolution in relation to the parametric predictive model. Additionally, the challenge of acquisition using the RGB-D multi-camera column system and 3D self-portraits for home implementation introduces the development of new techniques based on sparse-view approaches.

In the Health Sciences, the project aims to evaluate the impact of predictive models on patient motivation and adherence to treatment for obesity and overweight. Special emphasis will be placed on the positive effect of realistic predictive visualization of individual body shape on cognitive functioning and psychological well-being.

Scientific and technical impact will be disseminated through presentations at international conferences (ECCV, CVPR, IJCNN in 2022; IUNS-ICN, ICCV in 2023) and publications in high-impact international journals starting in 2023 (IJCV, TPAMI, Pattern Recognition, ASOC, CVIU, EJCN, IJBNP, and JN). Results will also be shared in open-access repositories such as RUA. Data and results will be managed under privacy regulations (LOPDGDD and ENS) and made publicly available on open servers for use by the scientific community, with participants' consent. Developed methods will be shared on repositories such as Bitbucket. Results will also be published on the Tech4Diet website.

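### The stated minimum of 35 per group does not give 80% power for the planned control-versus-experimental t-test: that needs 64 per group, and 35 gives about 54%.

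*Combined protocol and SAP*

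**What the plan says.** All of the sample-size justification is in one short paragraph of section 6, Study Design. After naming G*Power 3.1, it says: "A statistical power of 80%, a medium effect size (0.5), and a significance level (α) of 0.05 were established". The next sentence draws the conclusion: "Under these parameters, at least 35 participants per group were required to carry out the intervention". The test family, sidedness, effect-size metric, endpoint, pre-post correlation and any dropout allowance are not given.

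Under Selected Population, the document reports that "The sample consisted of a total of 133 Spanish volunteers" and that they were randomised to the two groups. It does not give the arm sizes.

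Under Data Analysis, Classical Statistical Analysis, the first entry for control versus experimental is "t-tests or ANOVA for continuous measures". The same list contains "ANCOVA to adjust for covariates (age, sex, baseline BMI") and, for the longitudinal analysis, "Repeated measures models (repeated measures ANOVA or mixed models"). None is designated primary. On incomplete data, the preprocessing list says "intent-to-treat analysis will be applied if missing data exceed 30"%, and Potential Limitations includes "Loss to follow-up in a 6-month intervention".

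**The concern.** The paragraph presents 35 per group as the result of three stated parameters. Those parameters, applied to a comparison of two independent groups, require nearly twice that number. The study is described as a trial of an experimental against a control group, so the between-group comparison is the one the sample size has to support.

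What is at stake is interpretation. The plan expects loss to follow-up and makes no allowance for it. A reader who takes 35 per group as sufficient could treat a heavily depleted sample as adequately powered and read a null result as evidence of no effect, when power for the stated effect was close to one half.

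**Working it through.** **Inputs.** From Study Design: power 0.80, effect size 0.5, alpha 0.05, 35 per group. From Selected Population: 133 in total. Assumed because not stated: 1:1 allocation (one per-group number is given), two-sided testing, and 0.5 as a standardised mean difference d. The alternatives are tried below.

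**Unadjusted two-group t-test.** Normal approximation: n per group = 2(1.960 + 0.842)² / 0.5² = 2 × 7.85 / 0.25 = 62.8, so 63. For the exact calculation, the t statistic has noncentrality d√(n/2) on 2n − 2 degrees of freedom:

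| n per group | noncentrality | critical t | power |
|---|---|---|---|
| 63 | 0.5√31.5 = 2.806 | 1.979 | 0.795 |
| 64 | 0.5√32 = 2.828 | 1.979 | 0.801 |
| 35 | 0.5√17.5 = 2.092 | 1.995 | 0.541 |

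The requirement is 64 per group, and the plan's figure of 35 is not reproduced. At 35 per group, 80% power is reached at d = 0.68 (noncentrality 0.68√17.5 = 2.845, power 0.801).

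**Other readings of the stated parameters.**
- One-sided: 51 per group (0.806; 50 gives 0.799). Power at 35 is 0.665.
- 0.5 as ANOVA f: with two groups d = 2f = 1.0, which needs 17 per group (0.807; 16 gives 0.781).
- Paired t-test within one group, standardised change 0.5: noncentrality 0.5√n, which needs 34 pairs (0.808; 33 gives 0.795). A signed-rank test, using its asymptotic efficiency of 3/π, needs 35. These land on or next to 35, but they test pre-post change in one group.

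**Analyses that use the baseline.** The plan gives no correlation, so each r below is an assumption.
- ANCOVA on the outcome's own baseline: effective d = 0.5/√(1 − r²), 67 degrees of freedom at 35 per group. Power is 0.663 at r = 0.5, 0.803 at r = 0.68 and 0.823 at r = 0.7. The 80% point is r = 0.677.
- Change score (equivalent to group-by-time with two visits): effective d = 0.5/√(2(1 − r)). Power is 0.541 at r = 0.5, 0.759 at r = 0.7, 0.801 at r = 0.73 and about 0.83 at r = 0.75. The 80% point is r = 0.729.
- ANCOVA on the three listed covariates, 65 degrees of freedom: they must explain R² = 0.459 of the outcome variance. The listed set contains the outcome's own baseline only when the outcome is BMI.

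**The 133 enrolled, unadjusted two-sided test, d = 0.5.** Noncentrality is d√(n₁n₂/(n₁ + n₂)).
- Split 66/67 with no loss: 0.816.
- The smaller arm must have at least 53 for 80%: 53/80 gives 0.800 and 52/81 gives 0.798.
- Near-even split with loss: power falls below 80% at about 4% loss (133 × 0.96 ≈ 128). It is 0.774, 0.724 and 0.665 at 10%, 20% and 30% loss.
- Loss that would leave 35 per group: 1 − 70/133 = 47%.

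**The case against.** The strongest reply is that the plan never ties 35 to an unadjusted t-test. It names no test in the sample-size paragraph, lists several analyses and makes none primary; coming first in a list is not a designation. The design has a pretest and a posttest, and a within-group calculation on the same inputs gives 34 or 35, so the software may have been used correctly for a different question. In addition, 133 were enrolled, more than the 128 needed, and no sentence in the document uses 35 as a target for completers.

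Much of this is fair. The firm finding is limited to the between-group test that the plan lists, together with the missing basis for 35. A paired origin is plausible but remains an inference. The enrolled number does cover the requirement if the split is near even and almost nobody is lost. The loss figures also apply only to the unadjusted test; a model that includes the outcome's own baseline would lose less.

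The reply does not rescue the figure. A within-group calculation does not power the comparison of randomised arms. The adjusted and change-score routes need a correlation or explained variance that is not among the stated parameters.

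**Conclusion.** The concern holds. With d = 0.5, two-sided alpha 0.05 and equal arms, the listed between-group t-test needs 64 evaluable participants per group, not 35. At 35, power is 54%, a shortfall of about 26 percentage points against the stated 80%. One-sided testing or the f metric does not recover 35. Baseline-adjusted or change-score analysis does so only at r of about 0.68 or 0.73, values the plan does not give. The conclusion rests on reading 0.5 as a standardised mean difference and on taking the control-versus-experimental comparison as the one to be powered. Enrolment of 133 is sufficient on paper (about 82% with a near-even split and no loss), but the margin is gone after about 4% loss. This is the document's only sample-size justification, so it should be corrected.

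**What to change.** Change the wording of the Study Design paragraph:

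1. Keep 35 as the figure originally calculated, and disclose the G*Power test, sidedness, effect metric and any correlation behind it.
2. Add, labelled as a correction and not as the original calculation: *For the unadjusted two-sided comparison of the randomised groups, d = 0.5, alpha 0.05 and 80% power require 64 evaluable participants per group (128 in total). Thirty-five per group gives 54% power, and 80% only for d = 0.68.*
3. State the actual split of the 133 and the unadjusted power it gives. With a near-even split and no loss this is about 82%, falling below 80% after about 4% loss and to 77%, 72% and 67% at 10%, 20% and 30% loss.
4. If 35 is to be defended through an adjusted or repeated-measures analysis, name that analysis and state the correlation assumed (about 0.68 for ANCOVA on the outcome's own baseline, about 0.73 for change scores).
5. State that 35 per group is not the benchmark for an adequate number of completers.

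Items 1 and 2 remove the contradiction; items 3 to 5 keep the number from being misused later. The cost is text only: no further participants and no change to the planned analyses. The stated position becomes less favourable than the present one.

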- Emotional Eating: Measured with the Emotional Eater Questionnaire (CCE) (Garaulet et al., 2012). Higher scores indicate greater influence of emotions on

food choices and eating habits.

- Prefrontal Symptoms: Assessed using the Prefrontal Symptoms Inventory (ISP-20) (Ruiz et al., 2012); the short version (Pedrero-Pérez et al., 2015) is a self-report questionnaire measuring cognitive, emotional, and behavioral alterations in daily activities.
- Impulsivity: Measured with the Barratt Impulsiveness Scale, BIS-II (Barratt, 1959), comprising 30 items divided into three subscales: cognitive impulsivity (8 items), motor impulsivity (10 items), and non-planning impulsivity (12 items).
- Health-Related Quality of Life: Assessed using the Short Form-12 Health Survey (SF-12) (Ware et al., 1996).
- Depression: Measured using the Beck Depression Inventory (BDI-II) (Beck, Steer & Brown, 1996).
- Life Satisfaction: Measured using the Satisfaction With Life Scale (SWLS) (Diener et al., 1985).

All questionnaire data were collected via Google Forms.

6. Technological and Body Image Variables

- **Body Image:** Assessed using the Body Self-Relations Questionnaire (MBSRQ – reduced Spanish version) (Botella et al., 2009). The instrument contains 45 items divided into two distinct parts: one evaluating general body image and another assessing satisfaction with specific body areas.
- **3D and 4D Images:** The 4D model represents morphological changes over time. Using wide-spectrum, low-cost 3D acquisition technologies (RGB-D sensors), a 4D model was constructed as the core of a human body visualization system, enabling accurate and realistic visualization over time. Throughout the intervention, morphological 3D images of participants were obtained, allowing them to observe their evolution through immersive Virtual Reality (VR) (only the experimental group observed these changes).

Morphological 4D images of participants in each session were captured using the 3D machine, composed of RGB-D devices for 3D image acquisition.

All anthropometric and clinical measurements were collected at the ALINUA Nutrition and Food Clinic, certified as a healthcare center affiliated with the Faculty of Health Sciences at the University of Alicante.

All questionnaires and the neuropsychological battery were administered at two time points: at the start of the program (initial session) and after six months of

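### Adverse effects are monitored by suspected cause, without stated like-for-like elicitation in controls or a summary by arm, so a control rate for dizziness, discomfort and anxiety is not assured

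*Combined protocol and SAP*

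**What the plan says.** All of the relevant text is in section 6 (Methodology).

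- **Monitoring Plan, scope.** What will be monitored is "Potential adverse effects arising from the use of Virtual Reality (e.g., dizziness, discomfort, anxiety) and the dietary program (e.g., malnutrition, minor side effects").
- **Monitoring Plan, handling.** "Adverse events will be recorded in a dedicated database and reported to the Ethics Committee if they are serious or unexpected". No arm is named. There is no event definition, collection schedule or grading.
- **Study Design, exposures.** "The experimental group received a specific, individualized dietary-nutritional intervention program combined with 4D virtual reality". "The control group received nutritional and physical activity education based on recommendations from a nutritionist".
- **Technological and Body Image Variables.** Of the VR display of body changes: "only the experimental group observed these changes".
- **Selected Population.** "The sample consisted of a total of 133 Spanish volunteers", and "Participants were randomly assigned to one of the two groups (experimental or control"). The allocation ratio is not given.
- **Data Analysis.** Control and experimental groups are to be compared with, among others, "Chi-square tests for categorical variables". Adverse events are named neither there nor among the data to be cleaned, which are clinical, anthropometric, psychological and neuropsychological.

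**The concern.** Dizziness, discomfort and anxiety are non-specific and can occur in adults who never wear a headset. Judging whether the intervention adds to them needs a control rate obtained in the same way. Randomisation supplies comparable groups, but it does not correct a difference in how hard events are looked for.

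A scope defined by suspected cause puts that control rate at risk. A control participant's dizziness cannot arise from VR that the participant never saw, so staff working from the stated scope have no instruction to ask about it. If events surface mainly in the experimental arm, background symptoms can look like harm. If staff must first attribute a symptom to VR or diet, real harm can be set aside as background.

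The only stated use of the event database is ethics reporting of serious or unexpected events. The named effects, when non-serious and expected, have no stated use. Any later statement on tolerability would rest on these data, and section 7 foresees transfer of the technology to healthcare institutions.

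**Working it through.** The documents give no adverse-event rate, safety sample size or safety power, so there is no plan figure to reproduce. The check is mainly textual, followed by a calculation of what a comparison by arm could show.

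**1. Which arm does each monitored exposure belong to?**
- *VR:* experimental arm only. This is explicit in Technological and Body Image Variables.
- *Dietary program:* Study Design uses the word program for the experimental arm's individualised intervention and describes the control arm as receiving education. Elsewhere, however, the start of the program marks the initial assessment of all participants. Experimental-only scope is therefore the natural reading, but an inference.

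**2. Is each named effect measured in both arms by another route?**
- *Malnutrition:* partly. Weight, body composition, muscle mass, total body water and 24-hour recalls are listed without restriction to an arm, and Study Design says that both groups had clinical and nutritional assessment at baseline and six months.
- *Dizziness, discomfort, anxiety:* no. The listed psychological instruments cover executive function, premorbid intelligence, emotional eating, prefrontal symptoms, impulsivity, quality of life, depression, life satisfaction and body image. None is described as measuring these three symptoms. The questionnaires are given only at baseline and six months, so they would not identify symptoms around a VR session.

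**3. Is a comparison of events by arm specified?** No. The generic chi-square test could be applied to event counts, but events are not listed as a variable.

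**4. What could a like-for-like comparison show?**

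Inputs: 133 participants (Selected Population); about 66 per arm (assumed, since the ratio is not stated); two-sided α = 0.05; target power 80%; control rates p₀ assumed at 1% to 20%.

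Power = Φ[(|p₁ − p₀| − 1.96·SE₀)/SE₁], where SE₀ = √(2·p̄(1 − p̄)/n), SE₁ = √(p₀(1 − p₀)/n + p₁(1 − p₁)/n) and p̄ = (p₀ + p₁)/2.

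Example with p₀ = 0.10, p₁ = 0.292, n = 66:
- p̄ = 0.196
- SE₀ = √(2 × 0.196 × 0.804/66) = 0.0691
- SE₁ = √((0.0900 + 0.2067)/66) = 0.0671
- (0.192 − 1.96 × 0.0691)/0.0671 = 0.84, so power = 0.80

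| Assumed control rate | Experimental rate detectable with 80% power | Difference (percentage points) |
|---|---|---|
| 1% | 13.6% | 12.6 |
| 5% | 21.4% | 16.4 |
| 10% | 29.2% | 19.2 |
| 20% | 42.4% | 22.4 |

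With no events among 66, the one-sided 95% upper bound on the true rate is 1 − 0.05^(1/66) = 4.4%. The chance of seeing at least one event is 1 − (1 − p)^66, which is 48%, 74% or 97% for true rates of 1%, 2% or 5%.

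A comparison by arm is therefore feasible but coarse, and an interval for the difference tells the reader more than a p-value alone.

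**The case against.** The strongest case against is that the plan is silent rather than wrong.

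- **The database sentence names no arm and no cause.** The scope sentence gives examples and does not say that nothing else counts. This stands: a reader might infer that events are collected in the experimental arm only, or that a causal judgement is required before an event is recorded, and the text states neither. What it does not supply is an instruction to ask controls the same questions. Storing events is not the same as eliciting them.
- **The dietary program may include the control arm's education.** This stands as a caveat. One-arm scope is explicit for VR only.
- **A chi-square comparison is available.** Also true. A reader might infer that events will never be compared by arm, but the documents only fail to specify it. A test cannot, however, repair unequal elicitation.
- **Randomised data relevant to harm exist in both arms.** Body composition, blood measures, blood pressure, diet recalls, depression score and quality of life are listed without arm restriction. To conclude that the trial cannot say anything about harm would therefore go too far. For dizziness or discomfort during a headset session, timing also gives some information without a control arm. Neither route gives a control rate for the three symptoms.
- **No false difference has been shown.** One could construct a case in which unequal collection alone yields a nominally significant result, but it would need an assumed background rate and an assumed number of control events, and the answer turns on the second. The documents give neither.
- **It may be late.** Study Design and Selected Population are written in the past tense, with the sample's ages reported, so some or all sessions may be over. This limits what can still be collected, but not what can be tabulated and caveated.

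**Conclusion.** The concern holds in a limited form. Monitoring is defined by suspected cause, like-for-like elicitation in both arms is not stated, and no adverse-event summary by arm is specified. For dizziness, discomfort and anxiety the trial is therefore not assured of a control rate against which to judge intervention harm. For malnutrition the gap is partial.

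The resulting bias cannot be sized from the documents. With about 66 per arm (assumed), even proper collection would have 80% power only for differences of roughly 13 to 22 percentage points over assumed control rates of 1% to 20%. The planned adherence and cognitive analyses are not affected. This is an inexpensive improvement to the safety data, and it governs how firmly any tolerability statement may be worded.

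**What to change.** 1. **Monitoring Plan.** State that all adverse events are recorded in both arms, whatever the suspected cause, with the same questions at the assessment and follow-up sessions still to come. The plan does not say whether both arms attend the same number of follow-up sessions. If they do not, base the comparison on the time points common to both.
2. **Data Analysis.** Add a table by randomised arm of participants with each named event, with any event, and with withdrawal due to an event. Give the difference in proportions with a confidence interval. The planned chi-square test may accompany it, or Fisher's exact test where counts are small. Say that only large differences are detectable.
3. **Participants who have finished.** Tabulate by arm what was recorded and state whether events were sought alike in controls. If they were not, draw no conclusion on safety or absence of harm from those data.

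The cost is a sentence or two in the Monitoring Plan, a few questions at existing visits and one table. The downsides are more minor control-arm events to log and a weaker safety statement for participants already completed. No treatment or visit is changed.
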